2.1.3.3 Tertiary/exploratory efficacy endpoint(s)

To address the tertiary objective of exploring the glycemic control and variability parameters in each treatment group at Week 12 using CGM, the following endpoints will be assessed:

- Mean hours per day in the glucose range of \geq 70 to \leq 180 mg/dL (\geq 3.9 to \leq 10 mmol/L),
- Percent time and mean hours per day in the glucose range of \geq 70 to \leq 140 mg/dL (\geq 3.9 to \leq 7.8 mmol/L) (on all-time and during the night [00:00 to 05:59]),
- Nocturnal [00:00 to 05:59] percent time in glucose range of \geq 70 to \leq 180 mg/dL (\geq 3.9 to \leq 10 mmol/L),
- Day time [06:00 to 23:59] percent time in glucose range of ≥70 to ≤180 mg/dL (≥3.9 to ≤10 mmol/L),
- Percent time and mean hours per day with glucose <54 mg/dL (<3.0 mmol/L) (on all time and during the night [00:00 to 5:59]),

- Percent time with glucose <70 mg/dL (<3.9 mmol/L) within the 12 hours after basal insulin injection,
- Percent time and mean hours per day with glucose >250 mg/dL (>13.9 mmol/L),
- Mean glucose profile over a 24-hour period,
- 24-hour Glucose Area Under the Curve (AUC mg/dL*minutes), derived using the trapezoidal rule. The derivation will be adjusted to be an hourly average (Section 2.5.2.1),
- Mean glucose,
- GMI,
- Percent time and mean hours per day in the glucose range of ≥54 to <70 mg/dL (≥3.0 to <3.9 mmol/L) (on all-time and during the night [00:00 to 05:59]),
- Percent time and mean hours per day in the glucose range of >180 to $\leq 250 \text{ mg/dL}$ (>10 to $\leq 13.9 \text{ mmol/L}$) (on all-time and during the night [00:00 to 05:59]).

Other tertiary/exploratory endpoints than those related to CGM:

- Daily insulin doses (total daily insulin, basal insulin, mealtime insulin, ratio of basal to mealtime insulin dose) in units and U/kg body weight at each visit. Change at Week 8 and Week 12 from baseline will be derived.
- Change from baseline to Week 12 in patient-reported outcomes (treatment satisfaction, sleep quality and quantity, and productivity) (for detail on PROs, see Section 2.1.7).
- 7-point SMPG profiles (pre-prandial and 2-hour postprandial plasma glucose at breakfast, lunch, dinner, and bedtime) at Week 12 and change in 7-point SMPG profiles from baseline to Week 12.

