2.5.1 General conventions

CGM days will be defined as starting/ending at 00:00/23:59 on the 24-hour clock. Only useable CGM days within the time windows (see Section 2.5.4) are used for derivation of CGM endpoints (primary and secondary).

Percentage time in range

The proportion of CGM readings falling into the range of \geq 70 to \leq 180 mg/dL [\geq 3.9 to \leq 10 mmol/L] from useable CGM (at least 10 useable days among the 20-day CGM within the time-window, see Section 2.5.4).

If there is missing data between two available measurements, linear interpolation will be performed to impute the time points with missing data. For example, if a glucose value is less than 70 mg/dL at 5 min, missing at 10 and 15 min then higher than 180 mg/dL at 20 min, the data at 10 and 15 minutes will be imputed using linear interpolation. Missing data at the start of the day and end of day will not be imputed.

Demographic formulas

- If the date of T1DM diagnosis is not missing, age at diagnosis will be calculated extracting the year from the date of the T1DM diagnosis and the year of birth:
 - a) Age at diagnosis (years) = YEAR (date of diagnosis) year of birth.
- Time since diabetes diagnosis will be derived:
 - a) Time since diabetes diagnosis (years) = Integer [(date of Informed Consent Date of Diagnosis + 1)/365.25].

Disease characteristics at baseline formulas

• Total daily insulin dose adjusted for body weight: Total daily dose (IU) / body weight in kg.

Physical examination formulas

- BMI (Quetelet index formula):
 - a) Weight (kg) / (Height (m) × Height (m))

where using height assessed at Screening Visit and body weight collected over the study.

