2.5.2 Data handling conventions for secondary efficacy variables

2.5.2.1 CGM secondary and tertiary endpoints

• mean hours per day = percent time × 24 hours

24-hour Area under the Curve (AUC24), derived using the trapezoidal rule based on AUCt (AUC over the CGM assessment period) and then divided by the number of days with usable CGM data. Trapezoidal rule:

a) $0.5 \times ($ glucose reading at time i + glucose reading at time i-1 $) \times ($ time i - time i-1).

Note: Missing values for calculation of AUC will be treated as not collected.

The following main secondary endpoints will be calculated as follows:

• Glucose total CV = 100% times square root of s_{total}^2 divided by the mean glucose \bar{y} . That is:

$$CV_{total} = 100 \times \frac{s_{total}^2}{\bar{y}}$$

with

$$s_{total}^{2} = \frac{\sum_{i=1}^{k} \sum_{j=1}^{n_{i}} (y_{ij} - \bar{y})^{2}}{N - 1}$$

and

$$ar{y} = rac{\sum_{i=1}^k \sum_{j=1}^{n_i} y_{ij}}{N}$$
 ,

where N is the number of total useable CGM data for each patient; k is the number of CGM assessment days; y_{ij} is the j^{th} CGM data from the Day i and n_i is the number of total useable CGM data within the Day i.

• Glucose between days CV = 100% times square root of $s^2_{between}$ divided by the mean glucose \overline{y} . That is:

$$CV_{between} = 100 \times \frac{s_{between}^2}{\bar{y}}$$

with

$$s^{2}_{between} = \frac{\sum_{i=1}^{k} (\bar{y}_{i} - \bar{y})^{2}}{K - 1}$$

where \bar{y}_i is the mean glucose for Day *i*:

$$\bar{y}_i = \frac{\sum_{j=1}^{n_i} y_{ij}}{n_i}.$$

Property of the Sanofi Group - strictly confidential

Page 39

VV-CLIN-0612739 1.0

01-Jul-2021 Version number: 1

• Glucose within days CV = 100% times square root of s^2_{within} divided by the mean glucose \overline{y} . That is:

$$CV_{within} = 100 \times \frac{s_{within}^2}{\bar{y}}$$

with

$$s^{2}_{within} = \frac{1}{K} \sum_{i=1}^{k} \frac{\sum_{j=1}^{n_{i}} (y_{ij} - \bar{y}_{i})^{2}}{n_{i} - 1}.$$

A Proc Varcomp procedure will be used to compute Glucose within days CV and Glucose between days CV for each patient where time point variability within each day is also accounted for

```
proc varcomp data =dsn;
by USUBJID avisit;
class ADY TIMEBIN;
model AVAL = ADY TIMEBIN;
ods output estimates=outstat;
run;
```

where:

AVAL: glucose value AVISIT: Analysis visit including Baseline and Week 12 ADY: Analysis day TIMEBIN: Timepoints

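### AUC24 is defined as the area over the whole CGM period divided by useable days only; coded as written, this inflates it whenever the integrated time includes excluded days

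*SAP*

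**What the plan says.** SAP 2.5.2.1 gives AUC24 in three parts.

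- **Numerator.** It is "based on AUCt (AUC over the CGM assessment period"). SAP 1.4 describes each CGM assessment as 20 consecutive days of wear.
- **Rule.** Each trapezoid is half of ("glucose reading at time i + glucose reading at time i-1") times the elapsed time between the two readings. The interval has no upper limit, and there is no restart at midnight. A note adds: "Missing values for calculation of AUC will be treated as not collected".
- **Denominator.** The area is taken "and then divided by the number of days with usable CGM data".

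Two other places bear on this.

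- SAP 2.5.1 sets CGM days from midnight to midnight. It states: "Only useable CGM days within the time windows" (with a pointer to the window table) "are used for derivation of CGM endpoints (primary and secondary"). AUC24 is listed as tertiary in SAP 2.1.3.3. The closing sentence of 2.5.2.1 extends the primary endpoint's derivation to exploratory endpoints, but only those that are percentages of time in a range.
- SAP 2.1.3.3 says of the AUC: "The derivation will be adjusted to be an hourly average (Section 2.5.2.1"). Section 2.5.2.1 contains no such step.

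**The concern.** An average per day needs the same days above and below the line. Here the area runs over the assessment period, while the divisor counts only days that pass the useability test. Removing an excluded day's readings does not remove its time: the last reading before the gap and the first one after it become neighbours, and the trapezoid between them is a day or more wide.

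Two patients with identical glucose could then have different AUC24 values because one lost more days in mid-recording. The same could happen within one patient between baseline and Week 12. Mean glucose divides by the number of readings, and GMI is a linear function of mean glucose, so neither has this problem. AUC24 could therefore contradict two other reported summaries of the same recording.

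**Working it through.** The documents state no AUC24 value, so there is no figure of the plan's own to reproduce. The check applies the written formula to a profile whose answer is known.

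**Inputs from the SAP**
- Readings: 288 per 24 hours, ie every 5 minutes (2.1.3).
- Nominal period: 20 days (1.4).
- Minimum useable days: "at least 10 useable days among the 20-day CGM within the time-window" (2.5.1).
- Week 12 target Day 64 to 84 (21 days); analysis window Day 57 to 91 (35 days) (2.5.4).

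**Assumption.** Glucose is constant at 160 mg/dL. The ratios do not depend on this level. The true 24-hour AUC is 160 × 1,440 = 230,400 mg/dL·min.

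**Three ways to code the definition**

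(a) Drop readings on excluded days and join what remains. With S days from the first to the last useable day and U useable days, the integrated time is (288 × S − 1) × 5 minutes, so

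factor = (288 × S − 1) × 5 / (1,440 × U), which is close to S/U.

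For S = 20 the integrated time is 28,795 minutes:

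| Useable days | Interior days excluded | Factor |
|---|---|---|
| 19 | 1 | 28,795 / 27,360 = 1.05 |
| 18 | 2 | 28,795 / 25,920 = 1.11 |
| 16 | 4 | 28,795 / 23,040 = 1.25 |
| 14 | 6 | 28,795 / 20,160 = 1.43 |
| 10 | 10 | 28,795 / 14,400 = 2.00 |

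(b) Integrate every reading in the period, because the useable-day rule names only primary and secondary endpoints. If the sensor recorded over the full 20 days, the factor is 20/U wherever the excluded days lie.

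(c) Integrate within each useable day only. Each day covers 287 × 5 = 1,435 minutes and gives 160 × 1,435 = 229,600, which is 0.9965 of the true value for every exclusion pattern. The 0.35% shortfall is the interval from 23:55 to midnight.

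**Position of the excluded days under (a)**
- Ten excluded days all at the start or all at the end: 1.00.
- Ten on alternate days, the last of them at the end: S = 19, so 19/10 = 1.90.
- Ten placed at random: mean 1.81, range 1.10 to 2.00 in 2,000 draws.
- First day, last day and one day in the middle excluded: 18/17 = 1.06.

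**Spans longer than 20 days.** Ten useable days spread across the 21-day target give 21/10 = 2.10. Across the 35-day window they give 35/10 = 3.50. The second is an arithmetic limit, not a likely case.

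**Varying glucose.** One simulated profile (mean 160, a daily wave of amplitude 40, day-to-day SD 15, reading SD 10, all assumed) gave 2.06 with 10 interior days excluded and 1.24 with 4. The factor then also depends on the two readings on either side of each gap.

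**Hourly average.** In the worst 20-day case AUC24 is 160 × 28,795 / 10 = 460,720. Dividing by 24 hours and then by 60 minutes gives 460,720 / 1,440 = 319.9 mg/dL, against a mean glucose of 160 from the same data. A plain division by 24 carries the inflation through. Division by the hours actually integrated would remove it for constant glucose. The SAP does not say which is meant.

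**The case against.** The strongest reply is that the SAP processes CGM by day throughout. Section 2.5.1 bounds CGM days at midnight, uses only useable days, and does not impute at the start or end of a day. Section 2.4.4.4 builds the mean 24-hour profile, another tertiary endpoint, from useable days. On that view AUCt is the area over useable days, the divisor matches it, and coding (c) follows. This is a sensible reading, and a careful programmer might well choose it. But it is not written: 2.5.2.1 refers to the assessment period, the filter in 2.5.1 does not name tertiary endpoints, and filtering out readings does not close the integral at the gap.

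The reply also has force on size. Sensors are inserted and devices collected at site visits (protocol 8.1.1.1 and Schedule of Activities). The 80% rule needs 0.8 × 24 = 19.2 hours of records. A sensor started after about 04:48 cannot give a useable first day, and one removed before about 19:12 cannot give a useable last day. Many exclusions will therefore fall at the ends, where coding (a) adds nothing. On the other hand, the sensor change after 10 days falls in the interior.

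Three stronger readings are tempting but unsupported.

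- A reader might infer that the reported AUC24 will be wrong. That depends on the program, which the documents do not show.
- A reader might infer that 2 is the ceiling. It is the worst case for a 20-day span only.
- A reader might infer that AUC24 would measure sensor failure instead of glucose. It would still scale with glucose, multiplied by a patient-specific factor.

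**Conclusion.** The point holds as a fault in the written definition. The numerator and denominator of AUC24 refer to different amounts of time, and no text in 2.5.1, 2.5.2.1 or 2.1.3.3 brings them into line. The inflation in the table rests on three conditions: literal coding, a 20-day span, and exclusions in the interior of the recording. With one interior day lost it is about 5%; doubling needs all ten excluded days to be interior.

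The consequence is limited. AUC24 is exploratory and summarized descriptively, and it lies outside the testing hierarchy in SAP 2.4.4.3. Time in range, total CV, mean glucose and GMI do not use this formula, so no confirmatory conclusion is touched. What is at stake is the correctness of one reported summary and its agreement with others from the same data.

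**What to change.** Rewrite the AUC24 entry in SAP 2.5.2.1 to state that:

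1. the area is computed within each useable calendar day (00:00 to 23:59), and readings are never joined across midnight or an excluded day;
2. each day's area is divided by the minutes actually integrated and scaled to 24 hours, which for the flat profile gives 229,600 / 1,435 × 1,440 = 230,400, the true value;
3. AUC24 is the mean of these values over useable days;
4. the hourly average is the same quantity scaled to 1 hour, with its unit stated.

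In SAP 2.5.1, extend the useable-day rule to tertiary CGM endpoints. Changing the divisor alone is not enough, because wide trapezoids across gaps would still give heavy weight to the two readings on either side.

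The cost is a few sentences and a small programming change. It needs no new data and does not affect any confirmatory analysis.

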2.5.2.2 Absolute change

Absolute change from baseline for all secondary endpoints will be calculated as follows:

• Absolute change from baseline on *X* at Visit i = (X at Visit i) - (X at baseline)

where X is a given secondary endpoint value, i is the post-baseline visit i and baseline is the last assessment before first administration of IMP.

2.5.2.3 HbA1c and FPG

HbA1c (mmol/mol) = (HgbA1C% - 2.15) × 10.929

```
FPG (mmol/mol) = FPG mg/dL \times 0.0555
```

2.5.2.4 WPAI

Employment status will be derived based on the coding rules for self-administration. That is, if Q1 = YES or Q1 = NO or missing and hours missed or worked > 0, then employed. If Q1 is missing and hours missed and worked = 0, then not employed.

The following scoring instruction is used to score the four subscales from the 6-item validated questionnaire WPAI-diabetes.

Four subscales:

- Absenteeism (Percent work time missed due to diabetes): Q2 / (Q2 + Q4)
- Presenteeism (Percent impairment while working due to diabetes): Q5 / 10
- Work productivity loss (Percent overall work impairment due to diabetes):

Q2 / (Q2 + Q4) + [(1 - (Q2 / (Q2 + Q4))) x (Q5 / 10)]

• Activity Impairment (Percent activity impairment due to diabetes): Q6 / 10

2.5.2.5 MOS Sleep

Values for Sleep Quantity (ie, the average number of hours sleep each night during the past 4 weeks) will be considered aberrant if they are >24. For these cases, the variable will be considered as missing.

2.5.3 Missing data

For categorical variables, patients with missing data are not included in calculations of percentages unless otherwise specified. When relevant, the number of patients with missing data is presented.

Handling of computation of treatment duration if investigational medicinal product end of treatment date is missing

For the calculation of the treatment duration, the date of the last dose of IMP is equal to the date of last administration reported on the Completion of End of Study/Follow-up case report form page. If this date is missing, the exposure duration should be left as missing.

Handling of medication missing/partial dates

No imputation of medication start/end dates or times will be performed. If a medication date or time is missing or partially missing and it cannot be determined whether it was taken prior or concomitantly, it will be considered a prior, concomitant, and post-treatment medication.

Handling of adverse events with missing or partial date/time of onset

Missing or partial adverse event onset dates and times will be imputed so that if the partial adverse event onset date/time information does not indicate that the adverse event started prior to treatment or after the treatment-emergent adverse event period, the adverse event will be classified as treatment-emergent. No imputation of adverse event end dates/times will be performed. These data imputations are for categorization purpose only and will not be used in listings. No imputation is planned for the date/time of adverse event resolution.

Handling of adverse events when date and time of first investigational medicinal product administration is missing

When the date and time of the first IMP administration is missing, all adverse events that occurred on or after the day of randomization should be considered as treatment-emergent adverse events. The exposure duration should be kept as missing.

Handling of missing assessment of relationship of adverse events to investigational medicinal product

If the assessment of the relationship to IMP is missing, then the relationship to IMP has to be assumed and the adverse event considered as such in the frequency tables of possibly related adverse events, but no imputation should be done at the data level.

Handling of missing responses of DTSQc and DTSQs

The total treatment satisfaction score is the sum of items 1, 4, 5, 6, 7 and 8.

If no more than 2 out of the 6 questions comprising the total treatment satisfaction score are missing, the total treatment satisfaction score is imputed by calculating the average of the scores from the answered questions, dividing this sum by the number of answered questions and multiplying the average by six.

If items 2 or 3 are not answered, the frequency of hypoglycemia or hyperglycemia scores is considered as missing.

Handling of missing responses of WPAI

If the patient is employed, and Q2, Q4 Q5, and Q6 is missing then the scores will be imputed using average of all scores from other patients who answer the questions. Otherwise, only Q6 will be imputed using average of all scores from other patients.

Multiple imputation for primary analysis

Multiple imputation under MAR assumptions

Once the missing data pattern will be assessed, the programming process for this primary analysis will follow three steps (if monotone missing pattern is observed for all patients, then proceed directly with Step 1b):

• Step 1a: Use PROC MI to produce a monotone missing data pattern. A monotone Monte Carlo Markov Chain MCMC imputation model will be used to impute interim missing data. A sample SAS code for this imputation is shown below:

```
PROC MI NIMPUTE=1000 DATA=orig OUT=impute1 SEED=14947 MIN=0 MAX=100;
BY ARM;
MCMC IMPUTE=MONOTONE;
VAR BASE PTIR;
RUN;
```

• Step 1b: Use PROC MI to execute the second imputation using the data set produced in the first imputation. A sample SAS code for this imputation is shown below (if Step 1a was not done due to monotone missing, then NIMPUTE=1000 and DATA=ORIG, BY statement not needed):

```
PROC MI NIMPUTE=1 DATA=impute1 OUT=impute2 SEED=14947 MIN=0 MAX=100;
CLASS ARM HBACRIT1;
BY _IMPUTATION_;
MONOTONE METHOD=REG
VAR ARM HBACRIT1 BASE PTIR;
RUN;
```

• Step 2: Each of the 1000 imputed datasets will undergo an ANCOVA using fixed categorical effects of treatment group (Toujeo, Tresiba), randomization stratum of screening HbA1c (<8.0% versus ≥8.0%), and the baseline percent time in range value 1 using the following ESTIMATE statement in PROC GLM

```
PROC GLM DATA=impute2;
BY _IMPUTATION_;
CLASS ARM HBACRIT1;
MODEL PTIR = ARM HBACRIT1 BASE;
ESTIMATE "TOUJEO-0.9 TRESIBA" INTERCEPT 0.1 TREAT 1 -0.9;
RUN;
```

• Step 3: The 1000 analysis results will be combined using PROC MIANALYZE (Rubin's rule). A sample SAS code for this combined analysis is shown below:

```
PROC MIANALYZE PARMS=est;
MODELEFFECTS estimate;
RUN;
```

In this SAS code above:

- orig: input dataset including one observation per patient in the ITT population
- BASE: Percentage of time in the glucose range of \geq 70 to \leq 180 mg/dL all time at baseline
- PTIR: Percentage of time in the glucose range of \geq 70 to \leq 180 mg/dL all time at Week 12

- ARM: treatment group as per randomized (TOUJEO/ TRESIBA)
- seed: the seed (14947) has been chosen arbitrarily and is based on the study code (LPS14947).
- HBACRIT1: randomization stratum of screening HbA1c (< 8.0% versus $\geq 8.0\%$)

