2.4.4.2 Analyses of secondary efficacy endpoints

Secondary efficacy endpoints analysis will be done on the ITT population, with no multiple imputation except for the main secondary endpoint 'Glucose total CV', for which a similar procedure as for the primary endpoint applies as it is part of the multiplicity procedure. No sensitivity analyses are planned for secondary endpoints.

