2.4.7 Analyses of quality of life/health economics variables

The analyses will be done on ITT population.

For DTSQs, MOS-Sleep, and WPAI, a descriptive summary of each score (see Section 2.1.7) will be done at baseline and at Week 12.

Change in DTSQs, MOS-Sleep, and WPAI scores from baseline to Week 12 will be analyzed using an ANCOVA model including the fixed categorical effects of treatment group (Toujeo, Tresiba), and the randomization stratum of HbA1c at screening (< 8.0%, $\geq 8.0\%$), as well as, the continuous fixed covariate of baseline score.

LS means and the corresponding SEs and 95% confidence interval by treatment for the change from baseline will be presented for descriptive purposes.

The DTSQc score will be analyzed using descriptive statistics at Week 12.

The DTSQc scores at Week 12 will be analyzed using an ANCOVA model including the fixed categorical effects of treatment group (Toujeo, Tresiba), DTSQs score at baseline, and the randomization stratum of HbA1c at screening (< 8.0%, $\geq 8.0\%$).

LS means differences in scores between treatment groups and its SEs and their corresponding 95% confidence interval of will also be evaluated.

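### Missing WPAI scores are filled with one average over other patients and then analysed as if observed, which shrinks any true arm difference and makes the by-arm confidence intervals too narrow

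*SAP*

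**What the plan says.** SAP 2.5.3 has a two-branch rule for WPAI. The first branch begins "If the patient is employed, and Q2, Q4 Q5, and Q6 is missing"; in that case "the scores will be imputed using average of all scores from other patients who answer the questions". The second branch reads: "Otherwise, only Q6 will be imputed using average of all scores from other patients". Neither branch says whose average is meant (own arm or both, which visit, which HbA1c stratum). The first does not say whether all of the listed items must be missing or any one of them.

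SAP 2.5.2.4 derives employment status from Q1 and the hours items and defines four scores. Absenteeism uses Q2 and Q4, presenteeism uses Q5, work productivity loss uses Q2, Q4 and Q5, and activity impairment uses Q6.

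SAP 2.4.7 gives the population ("The analyses will be done on ITT population") and the model: "Change in DTSQs, MOS-Sleep, and WPAI scores from baseline to Week 12 will be analyzed using an ANCOVA model", with treatment, HbA1c stratum and baseline score. The output is: "LS means and the corresponding SEs and 95% confidence interval by treatment for the change from baseline will be presented for descriptive purposes". SAP Appendix A repeats the by-treatment output for WPAI. A later sentence in 2.4.7 adds: "LS means differences in scores between treatment groups and its SEs and their corresponding 95% confidence interval of will also be evaluated". It follows the DTSQc text and does not name WPAI.

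Multiple imputation is planned for the primary endpoint. For secondary endpoints, SAP 2.4.4.2 says: "Secondary efficacy endpoints analysis will be done on the ITT population, with no multiple imputation except for the main secondary endpoint", which is glucose total CV. None is planned for WPAI, and no sensitivity analysis or variance correction is given for it. SAP 2.1.3.3 lists WPAI among the tertiary/exploratory endpoints.

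**The concern.** Filling a gap with the mean of other people treats a guess as a measurement. A filled Week 12 score carries no information on the patient's own treatment or baseline, yet it enters the ANCOVA as a full observation. Two consequences follow. If the arms truly differ, the filled patients pull both arm means toward a common value. The reported precision also reflects the number of patients in the table, not the number who answered.

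For a descriptive endpoint, an accurate estimate with an honest interval is the whole purpose of the analysis. The rule pushes toward little difference and overstates how well each arm's mean is known. It also cannot be programmed without further decisions on arm, visit and trigger.

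**Working it through.** The plan states no WPAI figure (no SD, effect, missing rate or power), so there is nothing to reproduce.

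**Inputs.** From the SAP: the fill rule (2.5.3), the ANCOVA (2.4.7), 1:1 allocation (1.1) and 169 randomized per group (1.3). Assumed: Week 12 scores missing completely at random at rate p = 5%, 10%, 22% or 30%; score SD 20; baseline to Week 12 correlation 0 or 0.5; true difference 0, 5 or 10 points; average pooled over both arms. The 22% is the plan's CGM non-evaluability assumption, borrowed as one point in the range.

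**Step 1: the difference.** Let y1 and y0 be the observed arm means, N the number per arm and s the SD. After filling with (y1 + y0)/2, the mean of arm 1 becomes (1 - p/2)·y1 + (p/2)·y0, and symmetrically for arm 0. The difference becomes (1 - p)(y1 - y0). The shrinkage depends on neither SD nor sample size.

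**Step 2: the by-arm interval (correlation 0, no true difference).**
- True variance of a filled arm mean: (s²/N)·(1 - p + p²/2)/(1 - p).
- Variance the analysis reports: about (s²/N)·(1 - p).
- Reported/true SE: √[(1 - p)²/(1 - p + p²/2)].
- At p = 0.22: √(0.6084/0.8042) = 0.870. Coverage is 2Φ(1.96 × 0.870) - 1 = 91.2%.

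| Missing | Difference / truth | By-arm reported/true SE | Coverage, formula | Coverage, simulated |
|---|---|---|---|---|
| 5% | 0.95 | 0.974 | 94.4% | 94.6% |
| 10% | 0.90 | 0.946 | 93.6% | 93.9% |
| 22% | 0.78 | 0.870 | 91.2% | 91.3% |
| 30% | 0.70 | 0.811 | 88.8% | 88.8% |

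The SE ratio contains neither N nor s.

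**Step 3: the interval for the difference, if reported.**
- True variance of the filled estimate: (1 - p)² × 2s²/[N(1 - p)] = 2s²(1 - p)/N.
- Reported variance: about 2s²(1 - p)/N, so the ratio is 1.
- Observed-case variance: 2s²/[N(1 - p)]. The filled interval is therefore (1 - p) times as wide at correlation 0.

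Coverage is lost through bias. At p = 0.22, s = 20, N = 169 and a true difference of 5, the SE is 20 × √(2 × 0.78/169) = 1.92 and the bias is 0.22 × 5 = 1.1. Coverage is Φ(1.96 - 0.57) - Φ(-1.96 - 0.57), about 91%.

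Simulated ANCOVA, correlation 0.5, 22% missing, 2,500 runs per row:

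| True difference | Filled: estimate, width, coverage | Observed-case: estimate, width, coverage |
|---|---|---|
| 0 | 0.02, 6.79, 94.9% | 0.05, 8.43, 95.0% |
| 5 | 3.84, 6.81, 89.8% | 4.95, 8.44, 94.2% |
| 10 | 7.83, 6.85, 75.6% | 10.05, 8.44, 94.6% |

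With no true difference, the rejection rate after filling was 5.1% in this scenario.

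**Step 4: the alternative.** Regression multiple imputation with arm and baseline, combined by Rubin's rules (500 runs, 30 imputations, correlation 0.5, 22% missing, true difference 5), gave an estimate of 4.95, width 8.46 and coverage 96.6%.

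**The case against.** The strongest reply is that little rides on this. WPAI is exploratory and its intervals are descriptive. Protocol 8.1.6 has questionnaires completed and returned on site, including by patients who stop treatment early, so the missing rate may be well below 22%. At 5% the effect is small. All of that stands and sets the priority.

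Four stronger readings are tempting, and the documents do not support them:

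- **A wrong SE or false-positive rate for the treatment difference.** Step 3 shows that the reported SE is about right for the filled estimator. It is small only against the observed-case SE. With no true difference, coverage stays near 95%. Filled patients do not lack residual variation either: in an ANCOVA with baseline, a constant Week 12 value still leaves a residual around the fitted line.
- **A plainly planned treatment-difference interval for WPAI.** The outputs clearly named for WPAI are by treatment. The sentence on differences follows the DTSQc text.
- **Single imputation found nowhere else in the SAP.** DTSQ totals are prorated from the answered items (2.5.3), and short CGM gaps are interpolated (2.1.3.1, 2.5.1). Those use the patient's own data, which is the relevant distinction.
- **Simulated coverage for the difference applies to all four scores.** The three work scores apply only to employed patients, so fewer than 169 per arm contribute. Proportional shrinkage and the by-arm SE ratio are unchanged, but lost coverage for the difference would be milder because bias divided by SE grows with √N. A wholly missing form may leave employment underivable, so the rule might then fill only Q6.

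Pooling over both arms is itself the plain reading of an incomplete text, not an explicit statement.

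**Conclusion.** The concern holds, at low priority. Followed as written, the rule gives a worse answer than leaving the scores missing. A true difference is reported at about (1 - p) of its size. The by-arm intervals under-cover even without a difference: slightly at 5% missing, to about 94% at 10% and 91% at 22%. An interval for the difference, if produced, is narrower than the observed-case interval and under-covers when a true difference exists, because it is centred on a diluted estimate.

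This rests on pooling over both arms, on filling at Week 12 only, and on missingness completely at random. The by-arm figures also assume correlation 0, and the simulated figures rest on an assumed SD and assumed effects. The shrinkage and the by-arm SE ratio depend on the missing rate alone under these assumptions, but that rate is not in the documents. The primary analysis and the three-step hierarchy are not affected.

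**What to change.** Delete the WPAI mean-imputation paragraph in SAP 2.5.3. Leave each score missing when the items it needs under SAP 2.5.2.4 are missing, fit the ANCOVA of 2.4.7 to observed scores, and report the number missing per arm and visit. State in 2.4.7 whether a treatment difference will be reported for WPAI.

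If imputation is wanted, use multiple imputation with arm, HbA1c stratum and baseline score, combined by Rubin's rules. Restrict it to employed patients for the three work scores. The code for the primary endpoint cannot be reused unchanged, because it would create work scores for patients who are not employed.

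The cost is one paragraph of SAP text and somewhat fewer patients in the WPAI tables.
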